The PD effects of IMR-687 from baseline to Week 36, as measured by the mean change from baseline in serum PD markers of erythropoiesis, iron metabolism, and hemolysis.	X	X
Mean change in transfusion burden expressed as either units of RBCs or mL/kg as a continuous variable during Week 12 to Week 24, Week 24 to Week 36, and Week 12 to Week 36, compared to the 12 weeks prior to Baseline (Day 1).	X	
The proportion of subjects who are transfusion independent for $\geq 8$ weeks during treatment.	X	
Mean change from baseline in TranQOL quality of life tool at Weeks 12, 24, and 36.	X	
Mean change from baseline in SF-36 quality of life tool at Weeks 12, 24, and 36.	X	X
Pharmacogenomic analyses of genes that may affect treatment response (including $\alpha$ -globin, gamma-globin XmnI polymorphism, and BLC11A).	X	X
Proportion of subjects who have an Hb increase of $\geq 1.0$ g/dL from baseline for $\geq 14$ days in the absence of RBC transfusions.		X
Proportion of subjects who are RBC transfusion-free over 36 weeks and other variables of transfusion burden.		X
Duration of the mean Hb increase from baseline of $\geq 1.0$ g/dL over 36 weeks.		X

Exploratory Endpoints (continued)	TDT	NTDT
Proportion of subjects who have an increase from baseline $\geq 1.5$ g/dL in mean of Hb values at Week 24 and Week 36 compared to baseline in the absence of transfusions.		X
Mean change from baseline in NTDT-PRO score over a continuous 12-week interval from Week 12 to Week 24 and Week 24 to Week 36.		X
Mean change from baseline in NTDT-PRO domain total score at Week 24.		X
Mean change in biomarkers from baseline to Week 36, stratified by genotype.	X	X

AUC = area under the concentration-time curve; AUC0-24 = AUC from time 0 to 24; Cmax = maximum plasma concentration; ECG = electrocardiogram; Hb = hemoglobin; HbF = fetal hemoglobin; LDH = lactate dehydrogenase; NTDT = non-transfusion dependent  $\beta$ -thalassemia; NTDT-PRO = non-transfusion dependent  $\beta$ -thalassemia patient reported outcome; PD = pharmacodynamics; PK = pharmacokinetics; pRBC = packed red blood cells; PRO = patient-reported outcome; RBC = red blood cell; SF-36 = Short Form (36) Health Survey; t1/2 = half-life; tmax = time to maximum plasma concentration; TDT = transfusion dependent  $\beta$ -thalassemia; TranQOL = transfusion-dependent quality of life.

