## 11.2. Preliminary Efficacy and Pharmacodynamic Assessments

### 11.2.1. Transfusion Burden

Transfusion burden will be assessed according the schedule of assessments ([Table 2](#) and [Table 3](#)) using the following variables: dates of transfusion events, number of pRBC units per event, volume and hematocrit of each pRBC unit, pre-transfusion Hb, and pre-transfusion weight. These variables may also follow the same documentation requirements outlined in [Section 11.1.5](#).

If a subject requires a transfusion on days when PK samples will be drawn (i.e., the Baseline [Day 1] or the Week 1, Week 3 [TDT]/Week 4 [NTDT], Week 24, or Week 36 visits), the transfusion can only be performed after the final PK sampling.

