- Change from Baseline in mean pre-transfusion Hb values at Weeks 12 to 24, Weeks 24 to 36, and Weeks 12 to 36 [using pre-transfusion Hb from the Historical Transfusion Burden and the Transfusion Burden CRFs]
- Proportion of subjects with an increase from Baseline of ≥ 1.0 g/dL in mean pre-transfusion Hb values or a Reduction in RBC Transfusion Burden ($\geq 33\%$ reduction) Endpoint at Weeks 12 to 24, Weeks 24 to 36, and Weeks 12 to 36 [using pre-transfusion Hb from the Historical Transfusion Burden and the Transfusion Burden CRFs]
- Time to first Hb increase (≥ 1.0 g/dL)

Two exploratory efficacy endpoints were modified:

- The mean change from Baseline in NTD-PRO score over a continuous 12-week interval from Week 12 to Week 24 and Week 24 to Week 36 was modified to the mean change from Baseline NTD-PRO total score and domain scores including tiredness/weakness and shortness of breath domains over a continuous 12-week interval from Week 12 to Week 24 and Week 24 to Week 36
- The mean change from Baseline in NTD-PRO domain total score at Week 24 was changed to the mean change from Baseline in NTD-PRO total score and domain scores including tiredness/weakness and shortness of breath domain scores at Week 24 and Week 36.

Per protocol, plasma concentrations of IMR-687 and metabolites could have been analyzed and used for PK analyses. The PK analyses for this study will only include IMR-687 plasma concentration-time data. No PK analysis of IMR-687 metabolites will be performed.

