8.1.1 Population 1: Transfusion-dependent β-thalassemia

For the secondary efficacy endpoint of percentage of subjects with hematologic improvement (reduction in transfusion burden), 30 subjects in an active treatment arm and 20 subjects in the placebo arm will provide approximately 79% power to detect a difference of 10% of subjects improving in the placebo arm versus 50% of subjects improving in an active treatment arm, using a two-sided alpha level of 0.05. No multiple comparisons adjustments will be made as these are secondary analyses.

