Mean change from Baseline in mean HbF values at Weeks 12 to 24 and Weeks 24 to 36 in the absence of transfusions.		X	
Proportion of subjects with an increase from Baseline of $\geq 3\%$ in mean HbF values at Weeks 12 to 24 and Weeks 24 to 36 in the absence of transfusions.		X	
Exploratory Endpoints		TDT	NTDT
The PD effects of IMR-687 from Baseline to Week 36, as measured by the mean change from Baseline in serum PD markers of erythropoiesis, iron metabolism, and hemolysis.	X	X	
Mean change in transfusion burden expressed as units of RBCs as a continuous variable during Week 12 to Week 24, Week 24 to Week 36, and Week 12 to Week 36, compared to the 12 weeks prior to Baseline (Day 1).	X		

The proportion of subjects who are transfusion independent for ≥ 8 weeks during treatment.	X	
Mean change from Baseline in TranQOL quality of life tool at Weeks 12, 24, and 36.	X	
Mean change from Baseline in SF-36 quality of life tool at Weeks 12, 24, and 36.	X	X
Pharmacogenomic analyses of genes that may affect treatment response (including α -globin, gamma-globin Xmn1 polymorphism, and BCL11A).	X	X
Proportion of subjects who have an Hb increase of ≥ 1.0 g/dL from Baseline for ≥ 14 days in the absence of RBC transfusions.		X
Proportion of subjects who are RBC transfusion-free over 36 weeks and other variables of transfusion burden.		X
Duration of the mean Hb increase from Baseline of ≥ 1.0 g/dL over 36 weeks.		X
Proportion of subjects who have an increase from Baseline ≥ 1.5 g/dL in mean of Hb values at Week 24 and Week 36 compared to Baseline in the absence of transfusions.		X
Mean number of transfusion events from Baseline to Week 24.	X	
Mean change from Baseline in NTDT-PRO tiredness/weakness (T/W) domain score over a continuous 12-week interval from Week 12 to Week 24 and Week 24 to Week 36.		X
Mean change from Baseline in NTDT-PRO total score and T/W domain score at Week 24 and Week 36.		X
Mean change in biomarkers from Baseline to Week 36, stratified by genotype. ^a	X	X
Time to first Hb increase (≥ 1.0 g/dL)		X

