13.6.6 Exploratory Efficacy Analyses

The PP Analysis Set will be used for all exploratory efficacy endpoint analyses. Selected analyses will be repeated on the ITT and/or mITT Analysis Sets as sensitivity analyses.

Table 11 Exploratory Endpoints – TDT Population

Exploratory Endpoints	Time Points	Exploratory Endpoint Analysis
The PD effects as measured by the mean change from Baseline in serum PD markers of erythropoiesis, iron metabolism, and hemolysis.	Baseline to week 36 (including all visits in between)	Mixed Model Repeated Measures (MMRM) analysis: Mean (95% CI), Mean difference (95% CI), and p-value will be provided.
Mean change in transfusion burden (pRBC units) as a continuous variable	Week 12 to Week 24, Week 24 to Week 36, and Week 12 to Week 36, compared to the 12-week prior to Baseline (Day 1)	Descriptive summary
Proportion of subjects who are transfusion-free (independent) for ≥ 8 weeks during treatment	Over treatment time	CMH analysis: Odds ratios (active arm vs. placebo), 95% CI, p-value, difference in proportions (active arm-Placebo) and corresponding 95% CI will be provided
Proportion of subjects who are RBC transfusion-free (independent) over 36 weeks and other variables of transfusion burden	Over 36 weeks	CMH analysis: Odds ratios (active arm vs. placebo), 95% CI, p-value, difference in proportions (active arm-Placebo) and corresponding 95% CI will be provided
Mean number of transfusion events	Baseline to Week 36	
 Summary statistics of the number of cumulative transfusions at every 3 weeks post-Baseline from Week 3 through Week 36. Analysis of Covariance (ANCOVA) analysis with Baseline value as a covariate: LSMean (95% CI), LSMean difference (95% CI) between each active dose and placebo, and p-value. Plots of the mean number of transfusions, mean number of units, and pre-transfusion mean Hb over time
Change from Baseline in mean pre-transfusion Hb values at Weeks 12 to 24, Weeks 24 to 36, and Weeks 12 to 36 [using pre-transfusion Hb from the Historical Transfusion Burden and the Transfusion Burden CRFs]	Baseline to Week 12 to Week 24, Week 24 to Week 36, and Week 12 to Week 36	
 Summary statistics for the Baseline, post-Baseline, and change from Baseline Hb by treatment arm Scatter box-whisker plots for mean change over continuous 12-week and 24-week intervals ANCOVA analysis with Baseline value as a covariate: LSMean (95% CI), LSMean difference (95% CI), and p-value.

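### In TDT, change in transfused units gets no between-arm estimate, interval or test, so burden in units is tested only through responder cut-offs; the optional mL/kg scale also disappears undeclared

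*SAP*

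**What the plan says.** Protocol Table 1 gives TDT an exploratory endpoint worded "Mean change in transfusion burden expressed as either units of RBCs or mL/kg as a continuous variable", for Weeks 12 to 24, 24 to 36 and 12 to 36 against the 12 weeks before baseline. The unit footnote in Protocol 8.1 makes the mL/kg calculation optional. On-study transfusion data include "volume and hematocrit of each pRBC unit, pre-transfusion Hb, and pre-transfusion weight" (Protocol 11.2.1). For the historical period these items are collected only where available (Protocol 11.1.5).

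SAP 9.0 has "Mean change in transfusion burden expressed as units of RBCs as a continuous variable". Table 11 repeats it as "Mean change in transfusion burden (pRBC units) as a continuous variable" and assigns a descriptive summary. SAP 13.6.6.1 specifies summary statistics and boxplots, and the subgroup version in 13.6.4.5 is also descriptive.

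SAP 6.1 states "Two exploratory efficacy endpoints were modified". Both are NTDT-PRO endpoints, and mL/kg is not mentioned.

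Inference on units comes from CMH tests of the 20%, 33% and 50% responder endpoints, each also requiring a reduction of at least 2 units (SAP 13.6.4.1). The number of transfusion events (13.6.4.1) and pre-transfusion Hb (13.6.6.1) are analysed by ANCOVA with baseline as covariate, giving LS mean differences, 95% CIs and p-values.

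**The concern.** Units transfused is the variable from which every responder endpoint is built, yet it is the one burden measure with no planned comparison between arms. The event-count ANCOVA does not fill the gap, because it cannot see a change in bags per transfusion.

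Several responder cut-offs do not fill it either. TDT entry requires more than 3 and up to 10 units in 12 weeks. In whole bags that is 4 to 10, so one bag is 1/10 = 10% to 1/4 = 25% of baseline. Since 20% of 10 bags is 2, the 2-unit floor makes the 20% endpoint in a 12-week window simply a reduction of at least 2 bags. For baselines of 4 to 6 bags, 33% is at most 1.98, so the 33% endpoint is the same event.

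At stake are an effect estimate in units per 12 weeks, which an odds ratio does not supply, and possibly power. The mL/kg omission is a smaller matter of traceability: someone comparing the documents cannot tell whether it was deliberate.

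**Working it through.** **Inputs (SAP 8.1.1).** "30 subjects in an active treatment arm and 20 subjects in the placebo arm", 10% v 50% responding, "using a two-sided alpha level of 0.05", and the plan "will provide approximately 79% power".

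**1. Reproduce the plan's figure.** Two proportions, pooled variance under the null, with continuity correction:
- pooled proportion = (20×0.10 + 30×0.50)/50 = 0.34
- SE under the null = √(0.34×0.66×(1/20 + 1/30)) = 0.1368
- SE under the alternative = √(0.09/20 + 0.25/30) = 0.1133
- corrected difference = 0.40 − 0.5×(1/20 + 1/30) = 0.3583
- power = Φ((0.3583 − 1.96×0.1368)/0.1133) = Φ(0.797) = 78.7%, matching 79%.

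The SAP specifies no continuity correction for the CMH test. The uncorrected CMH test has exact power 88.3%, and that is the comparator used below. Measuring the gain against 79% would overstate it.

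**2. Continuous comparison under a uniform shift.** Assume change in units is normal with equal SD in both arms and that the responder cut gives 10% and 50%. The arms then differ by z(0.90) − z(0.50) = 1.2816 SD. Noncentrality = 1.2816×√(n₁n₂/(n₁+n₂)), with n₁+n₂−2 degrees of freedom.
- 30 v 20: 1.2816×√12 = 4.44, 48 df
- 15 v 15: 1.2816×√7.5 = 3.51, 28 df. This is lower dose v placebo if all 60 subjects were allocated 1:2:1 (60/4 = 15); the earlier 2:1 phase would change it.

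| Active v placebo | Responder rates | Continuous | CMH (exact) | Gap, points |
|---|---|---|---|---|
| 30 v 20 | 10% v 50% | 99.2% | 88.3% | 11 |
| 30 v 20 | 10% v 40% | 93.7% | 66.7% | 27 |
| 30 v 20 | 10% v 30% | 72.9% | 36.1% | 37 |
| 15 v 15 | 10% v 50% | 92.3% | 67.3% | 25 |

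Simulated whole units confirm the first row (30 v 20, baseline 4 to 10, SD 1.2, shift 1.5; 10.5% v 50.2% responding): ANCOVA 98.5%, CMH 87.6%.

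**3. Relax the uniform shift.** Same whole-unit simulation, but only a fraction of active subjects benefits:

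| Active v placebo | Fraction, drop in units, SD | ANCOVA | CMH |
|---|---|---|---|
| 30 v 20 | 45%, 3, 1.2 | 77.6% | 78.8% |
| 30 v 20 | 50%, 2.5, 1.2 | 77.9% | 77.7% |
| 30 v 20 | 60%, 2, 1.2 | 80.6% | 74.1% |
| 15 v 15 | 45%, 3, 1.2 | 58% | 57% |
| 15 v 15 | 45%, 3, 1.5 | 47% | 41% |
| 15 v 15 | 45%, 4, 1.5 | 61% | 53% |

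Allowing about a point for simulation error, the gain is about −1 to +9 points.

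**The case against.** A reader might infer that TDT burden is tested only as yes/no. The documents do not support that: the number of transfusion events is a TDT secondary endpoint and is compared by ANCOVA without dichotomising. The point is confined to burden in units.

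A reader might also infer that the SAP dropped a protocol endpoint or weakened its analysis. It did neither. mL/kg was one of two permitted scales for a single exploratory endpoint, which survives in units. Protocol 13.6 plans listings and descriptive statistics for exploratory endpoints and names no test for this one. The primary objective is safety, and the sample size was not set by a statistical calculation. Asking for inference here is therefore an improvement to the plan, not the correction of a departure from the protocol.

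Finally, a large power loss from dichotomising cannot be claimed outright. The documents give no SD for change in units, and step 3 shows the advantage mostly disappearing when response is confined to a subset.

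All of this stands. It leaves untouched the absence of any between-arm estimate on units and the silence of SAP 6.1 on mL/kg.

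**Conclusion.** The point holds in a limited form. For TDT, change in pRBC units has no planned treatment difference, CI or test, although it bears on the first secondary objective and the SAP already applies the suitable model to two neighbouring variables. The assured benefit of changing this is an effect size with an interval in units per 12 weeks.

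The power benefit depends on the pattern of response. Under a uniform normal shift matching 10% v 50% it is 11 points at 30 v 20 and 25 at 15 v 15, and wider at 30 v 20 for weaker effects. If only a subset responds it is about −1 to +9 points. The documents cannot say which pattern applies.

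The mL/kg matter is an undeclared omission of an optional scale. Although volume, hematocrit and weight are on-study burden variables, change from baseline also needs historical volumes, so an mL/kg analysis could cover only a subset.

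**What to change.** In SAP Table 11 and 13.6.6.1, add an ANCOVA of change in units per 12 weeks for Weeks 13–24, 25–36 and 13–36, with treatment as factor and baseline units as covariate. Report LS mean differences, 95% CIs and nominal p-values for each active arm and the combined arms v placebo, as for transfusion events. In 6.1, either declare that mL/kg is not analysed and why, or restore it for subjects with historical volumes and state their number.

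Costs:
- No new data are needed. Three windows with three contrasts add 9 comparisons (18 if mL/kg is restored) to a plan without multiplicity adjustment, so label them exploratory and lead with the intervals.
- Scaling units by observed days to 84 extrapolates short follow-up. A subject leaving on Day 100 has 15 days in the window that opens on Day 86; one 2-unit transfusion would count as 2/15×84 = 11.2 units. State a minimum observed time, or add a check restricted to subjects who complete the window.

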13.6.6.1 TDT Population

PD Effects of Erythropoiesis, Iron Metabolism, and Hemolysis Endpoints

The mean changes from Baseline in serum PD markers of erythropoiesis, iron metabolism, and hemolysis will each be analyzed with an ANCOVA model with the corresponding Baseline value as a covariate. LSMean estimates and 95% CIs will be presented for each active arm and placebo at Week 36. The

LSMean difference estimates and associated 95% CIs and p-values at Week 36 will also be reported for each active arm vs. placebo and the combined active arms vs. Placebo.

Transfusion Burden Endpoints

Summary statistics of transfusion burden during the 12-week period prior to Baseline (Day 1) and the 24-week post-Baseline time period will be provided.

Boxplots illustrating the observed pRBC of transfused RBCs at Baseline, Week 12 to Week 24, Week 24 to Week 36, and Week 12 to Week 36 will be presented by treatment arm. Additionally, separate boxplots showing the change from the 12-week prior to Baseline (Day 1) timeframe to the Week 12 to Week 24 and Week 24 to Week 36 time periods and from the estimated 24-week period prior to Baseline (Day 1) to the Week 12 to Week 36 time period will be presented by treatment group. The estimated 24-week period prior to Baseline (Day 1) is the same estimate as calculated for the hematological improvement secondary endpoint.

Proportion of Subjects who are Transfusion Independent for ≥8 Weeks During Treatment Endpoint

The number and percentage of subjects who remain transfusion independent for at least 8 weeks during treatment will be tabulated, along with summary statistics of the duration of transfusion independence in weeks. The proportion of subjects who are transfusion independent for at least 8 weeks during treatment will also be analyzed using CMH tests. ORs, 95% CIs, and p-values will be reported. The difference in proportions (active arm-Placebo and the combined active arms-Placebo) and corresponding 95% CI will be also provided.

Number of Transfusion Events Endpoint

The mean number of transfusion events in IMR-687 arms from Baseline to Week 36 compared to placebo will be assessed using an ANCOVA model with baseline value as a covariate and treatment as a factor. Summary statistics of the number of cumulative transfusions at every 3 weeks post-Baseline from Week 3 through Week 24 will be presented. All post-baseline assessments of number of transfusions will be cumulative from baseline. For example, the number of transfusions at Week 24 and Week 36 will include all transfusions from baseline through the Week 24 and Week 36 visits, respectively. The least squares mean (LSMean) estimates and 95% CIs will be presented for each active arm and placebo at Week 24. Additionally, the LSMean difference estimates and associated 95% CIs and p-values at Week 36 will also be reported for each active arm vs. placebo and the combined active arms vs. Placebo.

Box whisker plots of the number of units, and pre-transfusion Hb with outliers over time will be provided by treatment arm.

Transfusion events data will be reported in a by-subject listing using the ITT Analysis Set.

Change from Baseline in Mean Pre-transfusion Hb Endpoint

The Baseline value of pre-transfusion Hb will be defined as the mean of the screening and baseline pre-transfusion Hb values from the Historical Transfusion Burden CRF. Post-Baseline pre-transfusion Hb is defined as the mean of all documented pre-transfusion hemoglobin values collected during each 12-week interval on the Transfusion Burden CRF. If there are any missing values at scheduled collected times, the mean will still be calculated from the remaining non-missing values. To estimate the pre-transfusion change of Hb after dosing within each 12-week interval (Week 12-24, week 24-36) and the 24-week interval (Week 12-36), summary statistics for the Baseline, post-Baseline, and change from Baseline pre-transfusion Hb will be provided by treatment arm.

Scatter box-whisker plots for the mean change in pre-transfusion Hb concentrations over continuous 12-week intervals from Week 12 to Week 24, Week 24 to Week 36, and Week 12 to 36 will be provided by treatment arm.

In addition, the change in mean pre-transfusion Hb concentrations over continuous 12-week intervals from Week 12 to Week 24, and Week 24 to Week 36 and 24-week intervals from Week 12 to Week 36 will be assessed using ANCOVA models with Baseline value as a covariate. Summary statistics for observed values at Baseline, Weeks 12-24, Weeks 24-36, and Weeks 12-36, and change from Baseline

to Weeks 12-24, 24-36, and 12-36 will be presented. LSMean estimates and 95% CIs will be presented for each active arm and placebo at Weeks 12-24, Weeks 24-36, and Weeks 12-36. The LSMean difference estimates and associated 95% CIs and p-values at Weeks 12-24, Weeks 24-36, and Weeks 12-36 will also be reported for each active arm compared to placebo and the combined active arms compared to Placebo.

Proportion of Subjects with an Increase from Baseline of ≥ 1.0 g/dL in Mean Pre-transfusion Hb or a Reduction in RBC Transfusion Burden Endpoint

The number and percentage of subjects meeting the following selected change in pre-transfusion Hb categories will be tabulated by treatment arm:

- Increase ≥ 1 g/dL
- Increase ≥ 1 g/dL OR $\geq 33\%$ reduction in RBC transfusion burden with a reduction of at least 2 units of RBCs (hematological improvement)

The proportion of subjects in meeting each criteria above (at Weeks 12 to 24, Weeks 24 to 36, and Weeks 12 to 36) will be evaluated using a Cochran-Mantel-Haenzel (CMH) test to compare the proportion of subjects who achieved improvement between the placebo group and each of the 2 active treatment arms (IMR-687 lower dose and IMR-687 higher dose) and the combined active arms. The number and percentage of responders and non-responders at Weeks 12-24, Weeks 24-36, and Weeks 12-36 will be presented for each treatment arm as well as ORs, 95% CIs, and p-values from the CMH tests. The difference in proportions (active arm-Placebo and the combined active arms-Placebo) and corresponding 95% CI will be also provided. Bar plots will be provided. The proportion of subjects with response in pre-transfusion Hb or hematological improvement at Weeks 12-24, Weeks 24-36, and Weeks 12-36 compared to Baseline, Odds ratios, 95% CI, and p values will be displayed by treatment arm.

Mean Change from Baseline in TranQOL and SF-36 Quality of Life Tools

Subjects in the TDT Population will complete two questionnaires, TranQOL and SF-36, at Baseline and at Weeks 12, 24, and 36.

The TranQOL includes 36 questions spanning five domains. Questions 1 – 10 will be used to calculate Physical Health domain scores, questions 11 – 24 will be used to calculate the Emotional Health domain score, question 25 will be used to calculate the Sexual Activity domain score, questions 26 – 30 will be used to calculate the Family Functioning domain score, and questions 31 – 36 will be used to calculate the School and Career Functioning domain score. Each of the 36 questions has five possible responses which will be coded numerically. For all questions except for items 2, 4, 9, 16, 17, 25, 26, and 27, responses and corresponding numerical values are:

- 5 = Always
- 4 = Often
- 3 = Sometimes
- 2 = Almost Never
- 1 = Never
- -1 = Not Applicable

For the remaining 8 questions, responses and corresponding numerical values are:

- 1 = Always
- 2 = Often
- 3 = Sometimes
- 4 = Almost Never

- 5 = Never
- -1 = Not Applicable

Domain scores are calculated using the equation $100 \times (1 - [(\text{Sum of all scores in the domain} - \text{number of valid responses in the domain}) / (\text{number of valid responses in the domain} \times 4)])$. Scores of -1 are excluded from the calculation. Domain scores can only be calculated if <25% of the total number of questions in that domain are missing. Domain scores range from 0 to 100 where higher scores indicate higher QoL.

Descriptive statistics for the five domain scores will be reported at Baseline and Weeks 12, 24, and 36. Change from Baseline to each post-Baseline assessment will also be presented for each domain score.

The SF-36 includes 36 questions spanning 8 scales which are weighted sums of the questions in their section. Optum Health scoring software will be used to transform individual question responses to the scales which range from 0 to 100 where higher scores indicate less disability. The scales include Physical Functioning, Role Physical, Bodily Pain, General Health, Vitality, Social Functioning, Role Emotional, and Mental Health. The software will also calculate two overall scores, the Physical Component Score and the Mental Component Score.

Descriptive statistics for the eight scale scores and the two component scores will be tabulated at Baseline and at Weeks 12, 24, and 36. Change from Baseline to each post-Baseline assessment will also be presented for each scale and component score.

By-subject listings of TranQOL data and SF-36 data will be presented on the ITT Analysis Set.

Average Number of Days Between Transfusions Endpoint

Descriptive statistics for the average number of days between transfusions over 36 weeks will be tabulated with the ITT Analysis Set. Tabulations will be repeated on the mITT (if available) and PP Analysis Sets.

